The sample size calculation for this hypothesis is based on the one-sample t-test for equivalence. The desired outcome is to reject the null hypothesis at the 0.025 significance level. For this equivalence test of bias, two comparisons will be performed: FloTrac vs Swan-Ganz and ClearSight vs Swan-Ganz. In order to preserve the overall type 1 error rate at 0.05, the Bonferroni Correction will be used to adjust for multiple comparisons. Assuming a true mean bias of 0.0 and a SD of 1.0 l/min in the cardiac output, the sample size required for δ =0.5, alpha=0.025, and power=90% to reject the null hypothesis is 45, ignoring the ICC. After considering ICC for eight repeated measures (m=8), adjusting for multiple comparisons, considering comparisons of between two target devices and a reference device pairs, simultaneously, a sample size of 60 Subjects is needed. After considering a 34.5% rejection rate for hemodynamic instability, 10% lost to follow-up rate, and 6 roll-in Subjects for the learning curve, up to 108 (102) evaluable Pivotal Subjects and 6 Roll-in Subjects) will be enrolled into the study.

By simulating the study results with a mixed effect model, using repeated measurement data collected from a similar study, although the sample size estimate from this approach is conservative, it is reasonable and rational.

2.3.2 Sample size consideration for percent error

The Critchley and Critchley method of percent error (PE) calculation will be compared to 30%. The Precision will be considered as acceptable if PE is less than or equal to 30%.

The hypothesis for PE is a one-sided test:

H0: PE > 30%H1: PE $\leq 30\%$

In a meta-analysis paper published in 2010, Peyton and Chong suggested that acceptable agreement should be a percentage error of 30% or less, which has become a widely quoted criterion.

[figure not shown]
In a paper published by Odor, Bampoe, and Cecconi, "PE is calculated by dividing the limits of agreement by the mean value of measurements taken using the reference method of CO monitoring in the required population. A PE cut of \pm 30% has been suggested as a pragmatic guide for clinicians to determine whether a new measurement technique represents a good alternative to the reference standard. The basis of this approach is that the level of precision should be at least equivalent to the reference standard i.e. thermodilution, which is \pm 20%. Since random error in measurement is compounded during combination of two precisions, with two measurements at \pm 20% equating to a total error of \pm 28.3%, the total PE is commonly rounded to \pm 30%. Thus, finding a percentage error THIRD PARTIES WITHOUT PRIOR WRITTEN PERMISSION OF EDWARDS LIFESCIENCES, LLC. II MUST NOT BE REPRODUCED OR DISCLOSED TO THOSO-0089208 Rev. A (This template is required by DOC-0089208)

	Revision Date: De	ecember 2, 2020	Rev	В	For Use Only by Affiliates of Edwards Lifesciences	Page 9
Edwards	Title	Statistical Analysis Pl Nonrandomized, Obso Monitoring in Pediatri	ervatio	onal St		

of less than \pm 30% equates to the new tested technique having an error similar to the reference standard, which should therefore be considered acceptable."

The sample size calculation for this hypothesis was based on the one-sided T-test. The desired outcome is to reject the null hypothesis at the 0.025 significance level. Assuming a true mean of 30% and a conservative SD assumption of 70%, the sample size required for power=90% to reject the null hypothesis is 49. With Bonferroni adjustment for two comparison between three target device systems, enrollment of 60 subjects is required.

Additionally, in the paper "A meta-analysis of studies using bias and precision statistics to compare cardiac output measurement techniques," Critchley LA and Critchley JA constructed an error gram from the percentage errors from the test and reference methods to determine acceptable limits between methods. They graphically showed that limits of agreement of up to +/-30% were acceptable for PE.

Because the study is designed with sub samples (repeated measurements) or sub sample sections (m=8), ICC is a factor needing to be considered in the sample size estimation. By similar assumption and calculation in section 2.3.1, for m=8, the SD=69.38%, the corresponding sample size necessary is 49. For PE, a sample size of n=60 will be used in the study design, after considering two pairwise comparisons between 2 devices with a reference device. In addition, after considering a, 34.5% rejection rate for hemodynamic instability, 10% lost to follow-up rate, up to 102 evaluable subjects will be targeted. To account for the learning curve, 6 additional roll-in subjects will be enrolled (up to 3 at each site), totaling 108 Subjects enrolled in the study.

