The sample size calculation for this hypothesis is based on the one-sample t-test for equivalence. The desired outcome is to reject the null hypothesis at the 0.05 significance level. For this equivalence test of bias, two comparisons will be performed: FloTrac vs Swan-Ganz and ClearSight vs Swan-Ganz. In order to preserve the overall type 1 error rate at 0.05, the Bonferroni Correction will be used to adjust for multiple comparisons.

THIS DOCUMENT CONTAINS CONFIDENTIAL AND PROPRIETARY INFORMATION OF EDWARDS LIFESCIENCES, LLC. IT MAY NOT BE REPRODUCED OR DISCLOSED WITHOUT PRIOR WRITTEN PERMISSION FROM EDWARDS LIFESCIENCES, LLC.

POGO Study
Study #2019-08

Assuming a true mean bias of 0.0 and a SD of 1.0 l/min in the cardiac output, the sample size required for δ =0.5, alpha=0.05, and power=90% to reject the null hypothesis is 45, ignoring the ICC. After considering ICC for eight repeated measures (m=8), a sample size of 54 Subjects in needed. After considering a 34.5% rejection rate for hemodynamic instability, 10% lost to follow-up rate and 6 Roll-in Subjects for the learning curve, a total of 102 (96 evaluable Pivotal Subjects and 6 Roll-in Subjects) will be enrolled.

Adjusting for multiple comparisons, considering there will be two target devices and a reference device pairs, simultaneously, 108 total Subjects will be enrolled in this study.

Sample size consideration for percent error

The Critchley and Critchley method of percent error (PE) calculation will be compared to 30%. The Precision will be considered as acceptable if PE is less than 30 %.

The hypothesis for PE is a one-sided test:

H0: PE > 30%H1: PE $\leq 30\%$

The sample size calculation for this hypothesis was based on the one-sided T-test. The desired outcome is to reject the null hypothesis at the 0.05 significance level. Assuming a true mean of 30% and a conservative SD assumption of 70%, the sample size required for power=90% to reject the null hypothesis is 49.

Because the study is designed with sub samples (repeated measurements) or sub sample sections (m= 8), ICC is a factor needing to be considered in the sample size estimation. When eight repeated measures (m=8) are performed, the SD=69.38%. The corresponding sample size necessary is 49.

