The sample size calculation for this hypothesis was based on the one-sample t-test for equivalence. The desired outcome is to reject the null hypothesis at the 0.025 significance level. Assuming a true mean bias of 0.0 and a SD of 0.85 l/min in the cardiac Index, the sample size required for δ =0.5, alpha=0.025, and power=90% to reject the null hypothesis is 33 ignoring the ICC. After considering ICC the sample size is also 33 for m=8. After considering a 34.5% rejection rate for hemodynamic instability, 10% lost to follow-up rate, and 6 roll-in subjects for the learning curve, up to 61 evaluable subjects will be enrolled. For two pairwise comparisons considering two target device with the reference device, the sample size is 108. For situations where variation from study subject is dominant, adding repeated measurements is not an efficient method in sample size estimation.

Adjusting cardiac output (CO) with study subject body surface area (BSA) results in the derivation of cardiac index (CI). This adjustment for body surface area, in the study pediatric population (12 to 18 years old), will result in a smaller bias and percent error between test device and reference device. The standard deviation estimate will also be smaller, at the same scale. By the result from publish literatures, the conservative median of BSA 1.2 is used in this adjustment, which will decrease the standard deviation. Thus, the sample size estimate decreases obviously.

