3.2.1 PE derived by CO

The percent error is derived as follow:

$$PE_{ij} = 100 * \frac{|CO_{tij} - CO_{rij}|}{CO_{rij}} = 100 * \frac{|x_{ij}|}{CO_{rij}}$$

where PE_{ij} is the percent error of ith subject at jth repeated measurement of FloTrac and ClearSight with CO measurements from the Swan-Ganz thermodilution pulmonary catheter, as the reference.

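### The 90% power claimed for the percent-error endpoint has no valid basis, because the assumed true value equals the null limit; related sample-size figures are mislabelled

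*Combined protocol and SAP*

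**What the plan says.** **Percent error.** SAP 2.3.2 sets H0: PE > 30% against H1: PE ≤ 30%, with a one-sided t-test at 0.025; SAP 8.2.1 names a one-sample t-test against the same limit. The planning assumption is "Assuming a true mean of 30% and a conservative SD assumption of 70%, the sample size required for power=90" (per cent). The result is 49, or 60 with Bonferroni. Protocol section 6 gives the same mean, SD and 49, but there "The desired outcome is to reject the null hypothesis at the 0.05 significance level". SAP 3.2.1 ("The percent error is derived as follow") defines PE for each matched pair as 100 × |CO test − CO reference| / CO reference.

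**Bias.** SAP 2.3.1 states "alpha=0.025, and power=90% to reject the null hypothesis is 45, ignoring the ICC", and after the ICC and multiplicity "a sample size of 60 Subjects is needed". SAP 2.3.3 states for cardiac index "alpha=0.025, and power=90% to reject the null hypothesis is 33 ignoring the ICC". Protocol section 6 gives 45 at alpha 0.05 and continues: "After considering ICC for eight repeated measures (m=8), a sample size of 54 Subjects in needed". After losses, "a total of 102 (96 evaluable Pivotal Subjects and 6 Roll-in Subjects) will be enrolled".

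**Totals.** At 90% power, SAP 2.3.5 lists 92 for bias and 102 for PE. SAP 2.3.2 and 2.3.5 describe the 102 as evaluable, with 6 roll-ins added to reach 108. SAP 5.2 defines an evaluable subject as one with non-rejected CO pairs who has completed the 30-day follow-up.

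**The concern.** A power statement needs an assumed truth inside the alternative. Here the assumed mean PE is exactly the limit to be beaten, so the design as described has no more chance of success than its false-positive rate. By SAP 2.3.5, PE is the larger of the two requirements behind 102 + 6 = 108, although the protocol and SAP 2.3.1 and 2.3.3 also attach 108 to bias. If the PE test fails, the plan offers no basis for telling poor precision from low power. Someone reading 102 as evaluable would also expect far more analysable subjects than the plan's own loss rates allow.

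**Working it through.** **1. PE as written.** Inputs: limit 30, true mean μ = 30, SD 70 (SAP 2.3.2, protocol section 6). For a one-sided one-sample t-test, the noncentrality is λ = √n × (30 − μ)/SD, and power = P(noncentral t with n − 1 df and noncentrality λ exceeds t(1−α, n−1)). With μ = 30, λ = 0, so power = α: 0.025 (SAP) or 0.05 (protocol) for n = 49, 60 or 102. No n gives 90%.

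**2. Where 49 and 60 come from.** Replace (30 − μ) by 30, i.e. μ = 0:
- n = 49, α = 0.05: λ = 7 × 30/70 = 3.00, power 0.905. This is the smallest n reaching 90%.
- n = 60, α = 0.025: λ = 7.746 × 30/70 = 3.32, power 0.904. Again the smallest n.
- n = 49 at the SAP's 0.025: power 0.836.

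So both figures treat 30% as a distance and imply a true PE of 0%. PE in SAP 3.2.1 cannot be negative, so a mean of 0 forces every value to 0 and the SD to 0. That contradicts SD 70%.

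**3. Power at a true PE below 30%.** The documents give no such value, so these are assumptions. All use n = 60 and one-sided α = 0.025.

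| True PE | SD 70, nominal t | SD 70, gamma | SD = 0.76 × mean, half-normal | SD = mean, exponential | SD = 1.5 × mean, gamma |
|---|---|---|---|---|---|
| 10% | 59% | 73% | – | – | – |
| 15% | 37% | 58% | – | – | – |
| 20% | 19% | 41% | 99.6% | 93% | 69% |
| 25% | 8% | 24% | 53% | 39% | 27% |

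The last four columns are simulated (200,000 runs). With SD proportional to the mean, power reaches 90% only at a true PE of about 22%, 20% or 17% or less, respectively.

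**4. Bias.** Two one-sided t-tests, δ = 0.5, true bias 0, power 90%:

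| SD | n at α 0.05 | n at α 0.025 |
|---|---|---|
| 1 (CO) | 45 | 54 |
| 0.991 (CO, ICC-adjusted) | 44 | 54 |
| 0.85 (CI) | 33 | 40 |
| 0.8425 (CI, ICC-adjusted) | 33 | 39 |

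The SAP's 45 and 33 are therefore alpha-0.05 sizes. At 0.025 each gives about 81% power. The ICC adjustment reduces the SD (√(0.98 + 0.02/8) = 0.991) and on its own moves 45 to 44. The step to 54 comes from alpha 0.025.

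**5. Losses.** Retention under the plan's rates is 0.655 × 0.90 = 0.5895.
- Bias: 54/0.5895 = 91.6, i.e. the 92 in SAP 2.3.5. The 60 in SAP 2.3.1 is not the bias requirement.
- PE: 60/0.5895 = 101.8, i.e. 102. So 102 is the count before losses, and 102 × 0.5895 = 60.1 would be evaluable.
- The protocol's 96 pivotal subjects give 96 × 0.5895 = 56.6, matching neither 54 nor 60.
- Neither 92 nor 102 contains the 6 roll-ins (with them, 98 and 108), although the note under SAP 2.3.5 says the table was adjusted for them.

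**6. Primary endpoint.** With 60 evaluable at α = 0.025, bias power per device is 0.936 (SD 1) or 0.940 (SD 0.991).

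**The case against.** The strongest reply is that nothing operational changes. PE is secondary, its test does not use the planning mean, the primary endpoint is adequately powered, and SAP 2.3.1 reaches 108 from bias alone. That is correct, and it limits the weight of the point. It does not make the stated 90% true.

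The SD-70 columns can also be challenged. A non-negative quantity with mean 10 and SD 70 is so skewed that no device would behave that way, and the plan never pairs that SD with such means. This is fair: those columns show only that the plan's own SD cannot support the claim. The proportional-SD columns are more plausible, and some of them exceed 90%.

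The 2.5% and 5% are nominal. With skewed data the t-test does not hold its level: gamma data with mean 30 and SD 70 reject in about 10% of runs at n = 60, and the three proportional-SD models reject in 3.8% to 7.1%. These are far from 90% too.

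Finally, rejected series are to be repeated, so 34.5% rejection need not remove that share of subjects. If every repeat succeeded, 102 × 0.90 gives about 92 evaluable, and proportional-SD power at a true PE of 20% would be about 99.9%, 98.5% and 83%. That is a possible outcome, but the plan sized the study by treating the 34.5% as lost.

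**Conclusion.** The concern holds. The 90% PE power is wrong as written in both documents, and the reading that reproduces 49 and 60 contradicts the definition of PE. Actual power cannot be stated from the documents, because they give neither a true PE below 30% nor an SD to match. Depending on those assumptions it runs from well under 50% to nearly 100% with 60 evaluable subjects. The labelling errors follow from exact calculation under the plan's own inputs: at alpha 0.025 the sizes are 54, 60 and 40 rather than 45, 49 and 33; the ICC does not explain 54; and 102 is an enrolment count. The finding casts no doubt on primary-endpoint power and gives no reason to change enrolment. It should be fixed because a stated power figure is false and the number of analysable subjects is overstated.

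**What to change.** Amend the text of the protocol and SAP; no subjects are added.

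- **PE power:** restate it at about 60 evaluable subjects for a justified true PE below 30%, with an SD consistent with the absolute PE and shown as a range. Otherwise withdraw the 90% claim.
- **Alpha labels in the SAP:** give 54 (CO bias), 60 (PE, if a 30-point distance is still shown) and 40 (CI bias) at 0.025, or label 45, 49 and 33 as alpha-0.05 sizes before Bonferroni. Carry the change through the 61 and 108 in SAP 2.3.3; with 40, 40/0.5895 = 67.9, so 68 + 6 = 74.
- **ICC:** delete it as the reason for 54 in the protocol.
- **Reconciliation:** align the 60 in SAP 2.3.1 and the protocol's 96 with the 92 in SAP 2.3.5, and correct that table's roll-in note.
- **102:** relabel it as enrolled pivotal subjects, expected to give about 60 evaluable under the plan's loss rates.

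The only cost beyond drafting is that the restated PE power may look less favourable.

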2.3.3 Sample size consideration for bias calculated with cardiac index

The bias between the matched pairs of CI measurements, as determined by the Bland-Altman method, must be smaller than the minimum clinical difference δ , which is the value that is large enough to claim difference.

[figure not shown]
The hypothesis for bias is:

H0: bias $<-\delta$ or bias $>\delta$

H1: $-\delta$ ≤ bias ≤ δ

Because there are no valid publications found through internet searching to design the settings in sample size estimation based on CI, the relation between CI and CO is used in sample size estimation here. Cardiac index (CI) is defined as cardiac output (CO)/body surface area (BSA). By the results from Cattermole G. N., Leung P. Y. M., Mak P. S. K. et al. 2010 and Cattermole G. N., Leung P. Y. M., Ho G. Y. L. et al. 2017, the BSA value for kid with age \geq 8 is greater than 1, target on Chinese population in Hong Kong. For the age group from 12 to 18 years, it is around 1.5. If the study subjects are from developed country the BSA value possibly will be larger. If the study targets at developing country population, this value possibly will be smaller. By this consideration BSA=1.2 is used in bias adjustment and the SD adjustment. The SD used in sample size estimation for CI will be 0.85 ($SD_{CI} \approx \frac{SD_{CO}}{BSA} \approx 0.85$).

In this study eight repeated measurements or sub sample sections for each study subject will be taken during the cardiac catherization case, thus intra-cluster correlation ecoefficiency ICC is a factor to be considered in sample size estimation. Here $ICC = \frac{\delta_s^2}{\delta_s^2 + \delta_{ss}^2}$. δ_s^2 is the variance component of study subject. δ_{ss}^2 is the variance component of sum sample. By literature the ICC in children ranges from 0.94 to 0.98. The variation of study subject is dominant. Fixed the study subjects, the more sub-samples taken the less δ_{ss}^2 will be by a factor 1/m. This will reduce the total variance applied in sample size calculation. Using ICC=0.98, and SD=1 (Variance=1) as an example, as an example, for m=8, the adjusted variance will be $0.98 * 0.7225 + (1-0.98) * \frac{0.7225}{8} = 0.70985$ and the SD=0.8425.

The sample size calculation for this hypothesis was based on the one-sample t-test for equivalence. The desired outcome is to reject the null hypothesis at the 0.025 significance level. Assuming a true mean bias of 0.0 and a SD of 0.85 l/min in the cardiac Index, the sample size required for δ =0.5, alpha=0.025, and power=90% to reject the null hypothesis is 33 ignoring the ICC. After considering ICC the sample size is also 33 for m=8. After considering a 34.5% rejection rate for hemodynamic instability, 10% lost to follow-up rate, and 6 roll-in subjects for the learning curve, up to 61 evaluable subjects will be enrolled. For two pairwise comparisons considering two target device with the reference device, the sample size is 108. For situations where variation from study subject is dominant, adding repeated measurements is not an efficient method in sample size estimation.

Adjusting cardiac output (CO) with study subject body surface area (BSA) results in the derivation of cardiac index (CI). This adjustment for body surface area, in the study pediatric population (12 to 18 years old), will result in a smaller bias and percent error between test device and reference device. The standard deviation estimate will also be smaller, at the same scale. By the result from publish literatures, the conservative median of BSA 1.2 is used in this adjustment, which will decrease the standard deviation. Thus, the sample size estimate decreases obviously.

2.3.4 Study subject allocation between age groups

In statistical analysis, balance study design have more analysis power, and interpolation is always much more dependable than extrapolation. For our study device there are more evidence available in the adult population. Considering study subject properties and two surgical sites, 6 roll-in subject will be tested in age group 12-18.

2.3.5 Target Sample Size Requirement

Power(%)	Bias (n)	PE (n)
90	92	102
85	81	87
80	75	79

(Note: original sample size estimate for Bias and PE were adjusted for Bonferroni (two pairwise comparisons), 34.5% rejection rate for hemodynamic instability, 10% lost to follow-up rate, and 6 roll-in subjects for the learning curve. The target sample will include 102 evaluable subjects. Six additional roll-in's will comprise the training cohort.)

	Revision Date: De	ecember 2, 2020	Rev	В	For Use Only by Affiliates of Edwards Lifesciences	Page 12
Edwards	Title	Statistical Analysis Pl Nonrandomized, Obso Monitoring in Pediatri	ervatio	onal St		

3. STUDY ENDPOINTS

The primary effectiveness endpoint is to demonstrate that monitoring of cardiac output (CO) with Swan-Ganz, FloTrac, and ClearSight is comparable as determined by the Bland-Altman method of bias.

The secondary endpoint analyses will include:

CO, assessed using include using the Critchley and Critchley method of percent error calculation

Two comparisons will be performed for each of three endpoints described above: FloTrac vs Swan-Ganz and ClearSight vs Swan-Ganz.

The primary and secondary efficacy endpoints will be analyzed using the evaluable analysis set as defined in Section 5.

The primary safety endpoint is to assess all serious intraoperative and post-operative adverse events through 30 days, including serious device-related events. The safety endpoint will be analyzed using the safety analysis set as defined in Section 5.

3.1 Primary effectiveness endpoint

By the CO measurement from Swan-Ganz, FloTrac, and ClearSight, and Fick principle, the variable bias (X) is derived for statistical analysis:

$$x_{ij} = CO_{tij} - CO_{rij}$$

Where x_{ij} is the bias of ith subject and jth matched pair repeated measurements, CO_{tij} is CO measurement of the ith subject at jth repeated measurement of test device, such as Swan-Ganz, FloTrac, and ClearSight, CO_{di} is the CO measurement of ith subject at jth repeated measurement of reference device the Swan-Ganz thermodilution pulmonary catheter. Here $i=1,\ldots,n$ (the estimated sample size, 102), $j=1,\ldots,m$ (the planned repeated measurements, 8).

3.1.2 97.5% Confidence Intervals for bias using bootstrap and limit of agreement methods

Bootstrap method will be used to estimate two-sided 97.5% confidence intervals for all CO and CI bias measures under study. This will be performed for all analysis datasets as well as those data with rejected data. Results will be compared.

Revision Date: December 2, 2020

Rev

For Use Only by Affiliates of Edwards Lifesciences

Page 13

Title

Statistical Analysis Plan for A Prospective, Single-Arm, Nonrandomized, Observational Study of Cardiac Output Monitoring in Pediatric Patients

3.2 Secondary effectiveness endpoints

$$PE_{ij} = 100 * \frac{|CO_{tij} - CO_{rij}|}{CO_{rij}} = 100 * \frac{|x_{ij}|}{CO_{rij}}$$

3.2.1 PE derived by CO

The percent error is derived as follow:

$$PE_{ij} = 100 * \frac{|CO_{tij} - CO_{rij}|}{CO_{rij}} = 100 * \frac{|x_{ij}|}{CO_{rij}}$$

where PE_{ij} is the percent error of ith subject at jth repeated measurement of FloTrac and ClearSight with CO measurements from the Swan-Ganz thermodilution pulmonary catheter, as the reference.

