8.1.3 Limits of Agreement

Limits of agreement will be computed using Bland-Altman methods. Components of the one-way analysis of variance will be used to estimate variance of multiple between-device differences for the same subject. These components of variance measures include the mean square for subjects (SS), and residual mean square (RMS). The differences between the average difference across subjects will be estimated from the difference between SS and RMS. This difference will be divided by $M=((\sum m_i)^2 - \sum m_i^2)/(n-1)^*(\sum m_i)$, where n=1 total number of subjects, and m_i is the number of pairwise difference measurements for the *ith* subject. The estimated component of variance, which represents the heterogeneity, is estimated as (SS – RMS)/M. The total variance (TV) for single differences on different subjects is estimated by the sum of these two components: TV = (SS – RMS)/M + RMS. The resulting lower and upper limits of agreement will be estimated with 97.5% confidence mean(diff) \pm 1.984*TV for a two-sided test.

Revision Date: December 2, 2020

Rev

For Use Only by Affiliates of Edwards Lifesciences

Page 22

Title

Statistical Analysis Plan for A Prospective, Single-Arm, Nonrandomized, Observational Study of Cardiac Output Monitoring in Pediatric Patients

В

We want agreement to be the same or at least similar over the range of CO and CI measurements. Plots of the difference bias between device pairings (ClearSight vs Swan-Ganz, and FloTrac vs Swan-Ganz), for CO and CI measurements, on average of the two device measurements will be performed, with reference lines including zero, mean difference, and lower and upper limits of agreement. Two-sided 97.5% LOA will be calculated for bias between device pairings⁹. The statisticians will determine whether the standard deviation of the mean difference is constant or non-constant for each measure. The mean difference and standard deviation about the mean difference will be estimated for all measurements. The difference measures will be tested for heterogeneity using components of variance methods. The variance for single differences between device pairs of measurements, on different subject, will be plotted. Also, mean difference will be plotted on the order in which observations are recorded for each subject.

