8.2 Secondary Endpoint

8.2.1 Percent Error calculated by CO as the secondary endpoint

The secondary endpoint of the percent error between the matched pairs of CO measurements as determined by the Critchley and Critchley method will be tested as below using the one sample t-test. The hypothesis for PE is:

H0: PE > 30% H1: PE ≤ 30%

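### Percent error is computed pair by pair as |test − reference|/reference but judged against a 30% limit that belongs to limits of agreement divided by mean CO, so the test is about twice as lenient as its stated criterion

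*Combined protocol and SAP*

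**What the plan says.** **Where the 30% comes from.** SAP 2.3.2 justifies the limit by citing a paper in which "PE is calculated by dividing the limits of agreement by the mean value of measurements taken using the reference method of CO monitoring". The figure is derived from two methods, each precise to ±20%, which combine to ±28.3% and are rounded to ±30%. The same section adds, of the Critchley and Critchley work, "They graphically showed that limits of agreement of up to +/-30% were acceptable for PE". Both statements concern limits of agreement, which give one value per device.

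**What is computed.** SAP 3.2 and 3.2.1 give a single formula: 100 times the absolute difference between test and reference CO, divided by that pair's reference CO. The accompanying text reads "where PE_{ij} is the percent error of ith subject at jth repeated measurement", so there is one value per matched pair.

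**What is tested.** Under SAP 8.2.1 the PE "as determined by the Critchley and Critchley method will be tested as below using the one sample t-test", with H0: PE > 30% and H1: PE ≤ 30%. SAP 2.3.2 sets the level at one-sided 0.025. Protocol section 6 gives the same hypothesis at 0.05.

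**What is not done.** SAP 8.1.3 computes limits of agreement, but no section divides them by mean CO or compares that ratio with 30%.

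**The concern.** The limit and the statistic are on different scales. A limit of agreement is roughly the 95% extreme of the differences, whereas a mean absolute error describes a typical difference. A bound set for the first is far too generous for the second. The t-test shows that the per-pair formula is meant literally: it needs one value per observation or subject, and the limits-of-agreement PE is a single number per device.

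This matters because the primary test (SAP 8.1.2) concerns mean bias only. A device can have zero mean bias and still scatter widely. SAP 8.1.3 reports limits of agreement without an acceptance limit, and SAP 8.4.1 is an exploratory bootstrap check against ±δ that validates the bias conclusion. The PE test is therefore the plan's only pass/fail test of precision, in a study meant to support wider indications for ages 12 to 18. A pass would be reported as meeting a published criterion that was not applied.

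**Working it through.** **Inputs from the documents.** Limit 30%; planning SD of PE 70%; power 90%; one-sided alpha 0.025 (SAP 2.3.2) or 0.05 (Protocol section 6); losses of 34.5% and 10%; target 102; planned bias 0 and SD of CO differences 1.0 L/min (SAP 2.3.1); ICC 0.98 with 8 repeats. **Assumed, because the documents do not give them:** normal differences, mean CO of 4 to 6 L/min, and a between-subject CV of CO of 0–30%.

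**1. The plan's own sample size.** A one-sided one-sample t-test with a 30-point difference, SD 70 and 90% power needs n = 49 at alpha 0.05 and n = 60 at 0.025. Then 60/(0.655 × 0.90) = 101.8, so 102. The stated 49, 60 and 102 all reproduce, but three points do not fit:
- The 49 belongs to alpha 0.05. At the SAP's 0.025 the answer is already 60.
- The calculation needs a true PE 30 points below the limit, yet the text reads "Assuming a true mean of 30% and a conservative SD assumption of 70"%, which puts the true mean at the limit. Read literally, power is about alpha.
- For a half-normal absolute error, an SD of 70% implies a mean of 70 × 0.798/0.603 = 93%, which cannot sit with a mean at or below 30%.

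**2. Ratio of the two definitions.** Let the differences have SD s and mean 0, and let mean CO be μ.
- Limits-of-agreement PE = 1.96 s/μ.
- Mean per-pair PE = √(2/π) s/μ = 0.798 s/μ.
- Ratio = 1.96/0.798 = 2.46.
- A per-pair mean of 30% equals 30 × 2.456 = 73.7% on the limits-of-agreement scale. A limits-of-agreement PE of 30% equals 30/2.456 = 12.2% per pair.

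With bias (folded normal) the ratio is 2.19 at bias 0.5 and SD 1.0 L/min, 2.02 at bias 0.5 and SD 0.75, and 1.68 at bias 0.5 and SD 0.5.

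**3. Effect once the t-test must reject.** The SD of |x| is 0.603 s. With ICC 0.98 the repeats add almost nothing, so the subject is the unit. Break-even solves (s/μ)(0.798 + t × 0.603/√n) = 0.30.
- n = 60, t = 2.001: s/μ = 0.30/0.954 = 0.315, so PE = 61.7%.
- n = 102, t = 1.984: s/μ = 0.30/0.916 = 0.327, so PE = 64.2%.

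Simulated chance of passing the SAP test (one-sided 0.025, zero bias, error SD the same at all CO, lognormal CO with mean 5 L/min):

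| True limits-of-agreement PE | CV of CO | n = 60 | n = 102 |
|---|---|---|---|
| 50% | 0 | 99% | >99% |
| 50% | 20% | 96% | >99% |
| 50% | 30% | 86% | 97% |
| 60% | 0 | 63% | 85% |
| 60% | 20% | 43% | 63% |
| 60% | 30% | 27% | 38% |

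Other scenarios at n = 60:
- Error proportional to CO (CV 20–30%): over 99% pass at PE 50% and 71–79% at PE 60%; half pass at 63–65%.
- Bias 0.5 L/min, CV 20%: 80% pass at PE 50% and 24% at PE 60%; half pass at about 55%.
- CV 30% with CO normal and truncated at 1.5 L/min instead of lognormal: 73% pass at PE 50%; half pass at about 54%.

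**4. At the plan's own SD of 1.0 L/min.** For mean CO of 4, 5 and 6 L/min, the limits-of-agreement PE is 196/4 = 49%, 196/5 = 39% and 196/6 = 33%, all above 30%. The SAP formula gives 79.8/4 = 20%, 79.8/5 = 16% and 79.8/6 = 13%, all well below it.

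**5. Connected text.**
- SAP 8.1.3, as printed in the text available, has the mean difference ± "1.984*TV for a two-sided test", where TV is the total variance, so a square root appears to be missing. At SD 0.5 the half-width would be 1.984 × 0.25 = 0.50 instead of 1.984 × 0.5 = 0.99. At SD 1.5 it would be 4.46 instead of 2.98.
- The multiplier 1.984 is the two-sided 95% t value on 101 df. The value for the stated 97.5% is 2.275.
- SAP 3.3.2 says PE for cardiac index equals PE for CO. That holds only because BSA cancels within a pair. It does not hold for the limits-of-agreement ratio when BSA varies, and it conflicts with SAP 2.3.3, which expects a smaller PE after BSA adjustment.

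**The case against.** PE is a secondary endpoint, and nothing in the plan makes study success depend on it. Limits of agreement and CO summaries will be reported, so a reader could form the conventional ratio. That stands, and it limits the harm, but a prespecified test reported as a pass still carries the wrong label.

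The verdict is wrong only for a device whose true PE lies between 30% and the effective limit; outside that band the two definitions mostly agree. That also stands. The documents do not give the devices' true PE, and the 1.0 L/min SD is a level that 19 of 21 cited studies did not exceed. It is nevertheless the SD the plan itself uses.

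The pass rates at 30% CV move with the assumed CO distribution: at a true PE of 50%, from 67% (normal CO truncated at 0.5 L/min) to 86% (lognormal). Individual percentages should therefore be read loosely, though every scenario examined is lenient.

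The missing square root might be lost in text extraction, although radicals survive in SAP 2.3.1. It and the multiplier label are separate from the test in 8.2.1 and matter here because the corrected PE would use those limits.

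Finally, the quoted convention asks for a PE below 30% and mentions no confidence bound. But the SAP frames this as a hypothesis test at one-sided 0.025, and an upper bound follows from that.

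**Conclusion.** The concern holds. That the statistic and the limit do not match is clear from the SAP's own text and needs no assumption. On point values the discrepancy is a factor of 2.46 with zero bias and normal differences, and 1.68 to 2.19 in the examples with bias of 0.5 L/min. With the t-test applied, the effective limit is about 54–65% at n = 60, roughly twice the stated 30%. These effective limits rest on normal errors, an assumed mean CO of 5 L/min and an assumed CV of up to 30%; the zero-bias ratio does not depend on mean CO. Because the prespecified rule can certify a device well outside the criterion it cites, it must be corrected before analysis.

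**What to change.** 1. In SAP 3.2, 3.2.1 and 3.3.2, define one PE per device: 100 × 1.96 × √TV / mean reference CO, with TV from the variance components in 8.1.3.
2. In 8.1.3, write the limits as the mean difference ± multiplier × √TV, and give one multiplier with its matching confidence label.
3. In 8.2.1, replace the t-test by a one-sided 97.5% upper bound from a bootstrap that resamples subjects (0.025 per device), with success if the bound is at or below 30%. Reconcile this with the 98.75% level in 3.4.1.
4. Keep the mean per-pair error as a descriptive statistic under another name. Compute PE for cardiac index from the cardiac index differences, and delete the statement that it equals PE for CO.
5. Restate the PE power in 2.3.2 and 2.3.5 at the existing sample size.

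The alternative is to keep the per-pair measure as the endpoint under its own name, with its own justified limit (about 12% is the zero-bias equivalent of 30%) and a new power calculation.

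**Cost.** SAP text, analysis code and a new power statement; no new data or enrolment. The criterion becomes much harder to meet. By a chi-square approximation with independent subjects, at n = 60 the observed PE must be at most 24.6%, and 90% power needs a true PE of about 22.1%. That is an SD of differences of 0.45, 0.56 or 0.68 L/min at mean CO 4, 5 or 6. At n = 102 the figures are 25.9% and 23.8%. At the planning SD of 1.0 L/min and mean CO of 4 to 6, the chance of success at n = 60 is below 1%. The sponsor should know this before the change is made.
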